### **5.7 Drug labelling**

---

The investigational product will have a label permanently affixed to the outside and will be labelled according with ICH/GCP and national regulations, stating that the material is for clinical trial / investigational use only and should be kept out of reach of children.

The bag with the dissolved solution will have an affixed label stating (in Norwegian)

This bag contains ... mg iron isomaltoside or placebo (Study drug number ...) dissolved in 100 ml NaCl 0.9 % for the IronIC trial. The drug is meant for intravenous administration over 30 minutes (1.67 ml/min). The content of this bag was prepared by ... .

Labels will also include blank lines (in Norwegian) for:

Patient's initials  
Patient's study number  
Date dispensed  
Name of prescribing doctor

"Denne posen inneholder ... mg jernisomaltosid eller placebo (studiemedikamentnummer ...) i 100 ml 0,9 % NaCl til bruk i IronIC-studien. Posen skal gis intravenøst i 30 minutter (1,67 ml/min). Denne posen ble tilberedt av \_\_\_\_\_.

Pasientens initialer: \_\_\_\_\_  
Studienummer: \_\_\_\_\_  
Dato: \_\_\_\_\_  
Forskrevet av dr: \_\_\_\_\_  
»

## 5.8 Subject identification

Each study participant is identified by a unique subject number that is assigned after the subject signs the informed consent form. This number is generated through the randomisation process. Once assigned, the subject number cannot be reused for any other subject. The same primary identifier will be used throughout the study.

# 6 Study procedures

## 6.1 Table

	Baseline		3 months	6 months
Informed consent	x	Study drug infusion		
Clinical examination	x		x	x
ECG	x			x
Echocardiography	x			
Safety samples 	x		x	x
Serum hCG 	x			
Randomisation	x			
Biobank samples 	x			x
6-minute walk test	x			x
Measurement of peak oxygen consumption	x			x
Hand grip strength	x			x
Body mass composition	x			x
Cognitive function	x			x
Quality of life	x			x
Adverse events		↔x↔		

Haematological parameters, renal function, serum electrolytes, tests of liver damage, TnT, NT-proBNP and CRP are measured routinely in our transplant recipients. In pre-menopausal women only Secondary endpoints (i.e. NT-proBNP, markers of iron metabolism and inflammation).

## 6.2 By visit

Study participants will be recruited from the pool of heart transplant recipients who attend regular follow-up at Oslo University Hospital, Rikshospitalet. A dedicated study nurse not responsible for the routine treatment of the patients, will ask eligible patients to participate when clinical assessment, ferritin/transferrin and safety blood samples (routine blood samples in heart transplant recipients) have been performed and analysed.

### **6.2.1 Before treatment starts**

---

#### *Informed consent*

Written informed consent (Appendix A) must have been provided voluntarily by each subject before any study specific procedure is initiated.

The following tests will be performed at baseline:

#### *Physical examination*

A physical examination (including examination of heart, lungs, abdomen, neck and assessment of peripheral circulation and oedema) must be performed; vital signs (blood pressure, and heart rate); and height and weight must be recorded.

#### *Medical history*

A medical history must be obtained, and age; gender; NYHA functional status; risk factors (hypertension, smoking, and diabetes); reason for and time since heart transplantation; and concomitant disease must be recorded.

#### *Concomitant medication*

All concomitant medication (incl. vitamins, herbal preparation and other “over-the-counter” drugs) used by the participant within 28 days of treatment start must be recorded in the CRF by generic name and dose.

#### *Laboratory analyses*

Blood samples will be obtained to determine: Haemoglobin; white blood cell count, platelet count; serum potassium; serum sodium; glucose, glycosylated haemoglobin (HbA1c); creatinine; ALT; bilirubin; albumin; INR; CRP; N-terminal pro-B-type natriuretic peptide (NT-proBNP); total cholesterol; ferritin; transferrin, serum iron and total iron binding capacity. Serum hCG must be evaluated to exclude pregnancy in pre-menopausal females, and repeated prior to study drug infusion if more than 72 hours have passed between screening and study drug administration. Blood for efficacy analyses must be drawn and appropriately labelled and stored for later analysis.

#### *Treadmill test*

A treadmill test for the assessment of peak oxygen consumption is performed at baseline. The results of this test will be used for adjustment of the test-result six months after study drug infusion. The latter result, with adjustment for the baseline result, constitutes the primary endpoint of the IronIC trial.

#### *Hand grip strength*

Right and left hand grip strengths will be measured by a hand-held dynamometer.

#### *Body composition*

Body composition (weight, total water, total fat, percent fat, the ratio of extracellular water to intracellular water [measuring oedema], and visceral fat) will be measured at baseline and after 6 months with the InBody 770 body composition analyser.

#### *Quality of life*

Self-reported, health-related quality of life will be gauged with the SF-36 and EQ 5D 3L questionnaires.

#### *Cognitive function*

Cognitive function will be assessed with the Cambridge Neuropsychological Test Automated Battery (CANTAB).

### **6.2.2 3-month safety visit**

---

The study participants will be asked to visit their general practitioner for a clinical examination and blood sampling 3 months after study drug infusion. The blood samples will be sent to the laboratory at Oslo University Hospital, Rikshospitalet, for delayed (after end-of-study) assessment of haemoglobin, serum ferritin, serum iron, serum transferrin, and transferrin saturation.

### 6.2.3 End of study visit

---

This study visit six months after study drug administration is designed to assess efficacy and safety.

#### *Medical history*

A medical history must be repeated, and NYHA functional status; any change in risk factors (hypertension, smoking, diabetes mellitus), and concomitant disease must be recorded. Any medical events since inclusion in trial must be evaluated. Current well-being, symptoms, potential side effects and physical capacity must be assessed.

#### *Physical examination*

A physical examination must be performed, and results (including examination of heart, lungs, abdomen, neck and assessment of peripheral circulation and oedema); vital signs (blood pressure, and heart rate); and height and weight must be recorded.

#### *Concomitant medication*

All concomitant medication (incl. vitamins, herbal preparation and other “over-the-counter” drugs) used by the participant within 28 days of treatment start must be recorded in the CRF by generic name and dose.

#### *Laboratory analyses*

Blood samples will be obtained to determine: Haemoglobin; white blood cell count, platelet count; serum potassium; serum sodium; glucose, glycosylated haemoglobin (HbA1c); creatinine; ALT; bilirubin; albumin; INR; CRP; N-terminal pro-B-type natriuretic peptide (NT-proBNP); total cholesterol; ferritin; transferrin, serum iron and total iron binding capacity. Blood for efficacy analyses must be drawn and appropriately labelled and stored for later analysis.

#### *Treadmill test*

A treadmill test for the assessment of peak oxygen consumption is performed after six months. The results of this test, with adjustment for the baseline result, constitute the primary endpoint of the IronIC trial.

#### *Hand grip strength*

Right and left hand grip strengths will be measured by a hand-held dynamometer.

#### *Body composition*

Body composition (weight, total water, total fat, percent fat, the ratio of extracellular water to intracellular water [measuring oedema], and visceral fat) will be measured at baseline and after 6 months with the InBody 770 body composition analyser.

#### *Quality of life*

Self-reported, health-related quality of life will be gauged with the SF-36 and EQ 5D 3L questionnaires.

#### *Cognitive function*

Cognitive function will be assessed with CANTAB.

#### *Safety assessment*

Any untoward medical event (i.e. any AE, SAE or SUSAR) since the last visit must be recorded in the case report form (CRF) and the patient medical record.

### 6.2.4 After end of treatment

---

We do not plan to perform study visits after the six-month follow-up.

### 6.3 Criteria for patient discontinuation

---

Patients may be discontinued from study treatment and assessments at any time. Specific reasons for discontinuing a patient for this study are:

- Voluntary discontinuation: participating patients are free to discontinue his/her participation in the study at any point in time, without prejudice to further treatment.
- Major protocol deviation
- Incorrect randomisation, i.e. the patient does not meet the required inclusion/exclusion criteria for the study
- Patient lost to follow-up
- Patient's non-compliance to study treatment and/or procedures

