### 6.4.1 Patient discontinuation

Patient withdrawal must be documented in the CRF as well as in hospital records. If possible, a final assessment should be obtained (end of study visit). The reason for discontinuation is recorded. The investigator is obliged to follow up any significant adverse events until the outcome either is recovered or resolved, recovering/resolving, not recovered/not resolved, recovered/resolved with sequelae, fatal or unknown. Patients who withdraw will be included in the intention-to treat analysis.

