### **10.3 Population for Analysis**

---

The following populations will be considered for the analyses:

- Intention to treat (ITT) population: All randomised participants, regardless of protocol adherence.
- Per-protocol population (PP): Includes all subjects who have received study drug

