#### **Key, secondary endpoints:**

The baseline-adjusted between-group difference in the change in i) hand grip strength, ii) normally distributed body composition data, and iii) other normally distributed data will be calculated by ANCOVA. The statistical null-hypotheses are that the changes in these characteristics do not differ between patients allocated to iron isomaltoside and patients allocated to placebo.

NT-proBNP, TnT and CRP at six months will be analysed using Mann Whitney U-tests, the statistical null-hypothesis being that the levels of these biomarkers do not differ between the treatment arms. Regarding quality of life, we specifically plan to assess the between-group number of patients with a minimal clinical difference in the SF36 score.

Secondary per protocol analyses will be performed using the same methods as for the intention-to-treat analyses. Exploratory analyses will be made for efficacy variables stratified by centre.

Safety analyses will include tabulation of type and frequency of all adverse events. Any serious adverse events will be reported with comprehensive narratives. Any value of safety laboratory parameters outside normal ranges will be identified.

Missing data will be omitted from analyses, i.e. there will be no imputation or estimation of missing values. Statistical analyses will be performed in IBM SPSS Statistics version 21 or later.

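### Protocol 6.3 allows a randomised patient's assessments to be ended for deviation, ineligibility or non-compliance; without a 6-month test that patient is lost from the primary intention-to-treat analysis

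*Protocol*

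**What the plan says.** - **Protocol 6.3** opens with "Patients may be discontinued from study treatment and assessments at any time". Besides voluntary withdrawal and loss to follow-up, it lists three reasons that do not come from the patient leaving: "Major protocol deviation", "Incorrect randomisation, i.e. the patient does not meet the required inclusion/exclusion criteria for the study" and "Patient's non-compliance to study treatment and/or procedures".
- **Protocol 6.4.1** covers what happens next: "If possible, a final assessment should be obtained (end of study visit"). It adds: "Patients who withdraw will be included in the intention-to treat analysis". Protocol 6.2.3 places the end-of-study visit at six months, and SAP 5.1 gives it a window of ± 2 weeks.
- **Protocol 10.3** defines the intention-to-treat population as "All randomised participants, regardless of protocol adherence".
- **Protocol 10.5**: "Missing data will be omitted from analyses, i.e. there will be no imputation or estimation of missing values". SAP 7.4 also rules out imputation. The exception is single missing items on quality-of-life forms (SAP 5.5), which does not touch the primary endpoint.
- **SAP 7.2.1** starts from all randomised patients, then limits the primary endpoint to those with an adequate exercise test at both baseline and follow-up, whether or not they received treatment.
- **Per-protocol set**: patients who received study drug (Protocol 10.3) and, in SAP 7.2.2, also did the baseline and follow-up tests. Neither definition names a deviation that excludes anyone.

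**The concern.** The intention-to-treat definition promises that adherence plays no part in who is analysed. The discontinuation rule lets the investigator end follow-up because of poor adherence, a deviation or late-discovered ineligibility. With no imputation, ending follow-up before the 6-month test also ends the patient's contribution to the primary analysis.

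The protection of randomisation is at stake. Deviations and non-compliance arise after allocation and may be related both to treatment and to exercise capacity. If they influence who has a 6-month value, the two analysed groups are no longer simply the groups that were randomised. Unlike deaths or withdrawn consent, these losses are avoidable, because the patient may be willing and able to return.

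**Working it through.** **1. What discontinuation can mean here.** Treatment is a single 30-minute infusion (Protocol 5.3), given immediately after randomisation (SAP 5.1). SAP 8.3 sees no treatment-compliance issue. After the infusion, the rule in 6.3 can in practice act only on assessments.

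**2. Following one patient through.** Suppose a patient is randomised, infused, and then discontinued from assessments for a major deviation.
- If the end-of-study visit is still held and the exercise test is adequate, the patient is analysed and no harm is done.
- If it is not held, there is no 6-month value (Protocol 6.4.1 makes the visit conditional), none is imputed (Protocol 10.5, SAP 7.4), and the patient is outside the primary ANCOVA (SAP 7.2.1, 9.1).

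In the second case, neither inclusion of all randomised patients (Protocol 10.3) nor inclusion of those who withdraw (Protocol 6.4.1) can be honoured for the primary endpoint. The sentence in 6.4.1 also speaks of patients who withdraw, so its cover for those discontinued by the investigator is unclear.

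**3. Would a planned analysis reveal the effect?** The per-protocol set needs the follow-up test too, so the same patient is missing from both analyses. SAP 7.4 compares the baseline data of completers and drop-outs and looks at dropout by arm. It does not re-estimate the treatment effect under other assumptions about the missing values.

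**4. The plan's own sample size.** Inputs from Protocol 10.1 and 10.5: difference 1.5, SD 2.5 ml/kg/min, two-sided 5%, power 80%.

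n per group = 2 × (1.960 + 0.842)² × 2.5² / 1.5² = 2 × 7.85 × 2.778 = 43.6, so 44. The plan's figure is reproduced, with power 80.4% at 44 per group. A t-based calculation gives 44.6 per group, and 79.5% power at 44.

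**5. The margin for losses.** 100 enrolled − 2 × 44 = 12. The plan states no dropout rate, so the losses below are assumed.

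| Patients without an analysable test | Power (normal approximation) |
|---|---|
| 0 | 85.1% |
| 6 | 82.9% |
| 12 | 80.4% |
| 16 | 78.5% |
| 20 | 76.5% |

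Power stays at the planned level for up to 12 losses from all causes.

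**6. Size of a possible shift.** If a fraction m of one arm is removed, and those patients differ by k from those retained after baseline adjustment, that arm's mean shifts by m × k. The documents give neither m nor k; the values here are assumptions.
- m = 5%, k = 1.5: 0.05 × 1.5 = 0.075 ml/kg/min; 0.075 / 1.5 = 5% of the target.
- m = 10%, k = 3: 0.10 × 3 = 0.30 ml/kg/min; 0.30 / 1.5 = 20% of the target.

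In an arm of 50 this is 2.5 to 5 patients. Removals in the other arm would offset or add to the shift; the net shift is the difference between the two products.

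**The case against.** The case against is substantial. Section 6.3 is permissive and removes nobody automatically. Section 6.4.1 asks for the end-of-study visit, which 6.2.3 places at six months, and intends that patients who withdraw stay in the intention-to-treat analysis. The SAP does not use adherence as a criterion: 7.2.1 asks only for adequate tests, 8.3 keeps patients whose infusion was incomplete, and 8.1 gives death, withdrawn consent and failure to attend as examples of drop-out reasons. Population status is fixed before unblinding (SAP 7.2.3), and investigators are blinded (Protocol 10.2.3). Ineligibility concerns status at entry, so under blinding its discovery should not differ by arm.

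Most of this stands. It rules out reading 6.3 as automatic deletion, or adherence as a formal test for entry to the analysis set. It does not close the gap: no text requires the 6-month test after a deviation, ineligibility or non-compliance, and the visit remains conditional. Blinding prevents decisions made on knowledge of the arm, but not decisions prompted by events that differ between arms.

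A reader might also infer that the usual deviation would be iron use, that it would be commoner on placebo, and that removing those patients would raise the placebo mean. The documents do not support this. Protocol 5.5.1 prohibits iron but does not call its use a major deviation, and no rate is given by arm. The 3-month iron samples are assayed only after the end of the study (Protocol 6.2.2). If iron works as hypothesised, a placebo patient who took it could have a higher 6-month value, so the direction could be the reverse.

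**Conclusion.** The point holds as a conflict in the plan's wording that permits avoidable loss of randomised patients. Protocol 6.3 allows assessments to end for reasons of conduct or eligibility, and any patient so discontinued without an adequate 6-month test leaves the primary ANCOVA, contrary to the intention-to-treat definition. It does not show that patients will be lost in this way, or which arm would gain.

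The shift of 0.08–0.30 ml/kg/min (5–20% of the 1.5 target) is an illustration. It assumes removals of 5–10% in one arm only and a difference of 1.5–3 ml/kg/min that persists after adjustment for baseline peak oxygen consumption. Smaller or balanced removals would matter less. Power is not the main issue while total losses stay at 12 or fewer. The change should be made because the rule works against the plan's own stated principle and correcting it costs little.

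**What to change.** - **Protocol 6.3 and 6.4.1:** state that only withdrawal of consent for assessments, death or loss to follow-up ends assessments. Patients with a protocol deviation, ineligibility found after randomisation, or non-compliance are still invited to the planned assessments at 6 months ± 2 weeks and are analysed in the arm to which they were randomised. This concerns data collection only and sets no treatment rule.
- **Recording:** document each deviation.
- **Per-protocol set (Protocol 10.3, SAP 7.2.2):** if deviations are to be examined there, amend the definition before unblinding to name those that exclude a patient. The current definition excludes none, so it cannot serve that purpose as written.

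The cost is wording in the protocol and SAP, the approval step for amendments in Protocol 11.3, and some effort to retain these patients. No visit is added, because the 6-month assessments are already planned for everyone.

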## 6.4 Procedures for discontinuation

---

### 6.4.1 Patient discontinuation

Patient withdrawal must be documented in the CRF as well as in hospital records. If possible, a final assessment should be obtained (end of study visit). The reason for discontinuation is recorded. The investigator is obliged to follow up any significant adverse events until the outcome either is recovered or resolved, recovering/resolving, not recovered/not resolved, recovered/resolved with sequelae, fatal or unknown. Patients who withdraw will be included in the intention-to treat analysis.

### 6.4.2 Trial discontinuation

The whole trial may be discontinued at the discretion of the primary investigator or the sponsor in the event of any of the following:

- Occurrence of AEs unknown to date in respect of their nature, severity and duration
- Medical or ethical reasons affecting the continued performance of the trial
- Difficulties in the recruitment of patients
- Cancellation of drug development

The sponsor and principal investigator will inform all investigators, the relevant Competent Authorities and Ethics Committees of the termination of the trial along with the reasons for such action. If the study is terminated early on grounds of safety, the Competent Authorities and Ethics Committees will be informed within 15 days.

## 7 Assessments

---

### 7.1 Assessments of efficacy

Efficacy will be evaluated through a comprehensive assessment of peak oxygen uptake, hand-grip strength, self-assessed quality of life, assessment of cognitive function, and biochemistry. All efficacy assessments will be made prior to study drug infusion and at the end-of-study visit after six months. The results will be reported as baseline-adjusted between-group differences.

#### 7.1.1 Peak oxygen consumption

Peak oxygen consumption will be measured on a treadmill according to a protocol that we have successfully employed in heart transplant recipients. The protocol employs a modified treadmill walk test in compliance with the European Society of Cardiology recommendations for cardiopulmonary exercise testing in patients with chronic heart failure. The test begins with warm-up period of 10 min on a Runrace Treadmill (Technogym, Cesena, Italy), during which the individual walk speed is determined. The inclination of the treadmill is then increased by 2% every 2 min until volitional fatigue. Test termination criteria are a respiratory exchange ratio (RER) >1.05 and/or a rated perceived exertion (Borg 6–20 scale) >18. Lung function and breath gas exchange will be measured using the Sensormedics Vmax (Yorba Linda, CA, USA). ECG and HR will be monitored

before, during and after exercise. Peak oxygen consumption, carbon dioxide production, maximum ventilation and respiratory exchange rate will be continuously monitored. Blood pressure will be measured automatically (Tango; Sun Tech Medical Instruments, NC, USA) before exercise, every 2 min during exercise, and after exercise. After termination of the test, the treadmill will be stopped and the patients rest in an upright position for a recovery period of 2 min. VO2peak will be calculated as the mean of the three highest ten-second measurements before volitional fatigue prior to the end of exercise. A Borg score >18 and/or a respiratory exchange ratio > 1.05 will be used as criteria for an adequate maximal exercise test.

#### **Summary of parameters to be recorded:**

Before start: Heart rate, oxygen saturation and blood pressure. At peak exercise: treadmill inclination, heart rate, blood pressure, Borg score, oxygen saturation, peak oxygen consumption, expiratory exchange ratio, and peak ventilation volume.

#### **7.1.2 Hand grip strength**

---

As an estimate of muscle strength, we will measure peak hand grip strength using a hand grip strength dynamometer.

